5.4.1.2 Prophylaxis for Tumor Lysis Syndrome and Tumor Flare

All patients should receive prophylaxis for TLS before the initiation of therapy. Prophylaxis will include appropriate hydration, administration of an agent to reduce uric acid, such as allopurinol

(or rasburicase IV for high risk patients with elevated uric acid levels before treatment). Laboratory results including electrolyte values will be assessed on a weekly basis during cycle 1 of treatment. If tumor flare occurs, symptomatic treatment will be up to the discretion of the investigator. For grade ≤ 2 symptoms, study drug can continue without dose modification along with symptomatic treatment with NSAIDS. For grade 3/4 symptoms, dose interruption and treatment with NDAIDS and steroid is recommended.

5.4.1.3 Prophylaxis for HBV Reactivation in Asymptomatic Carriers

All patients must be screened for hepatitis B before starting treatment. Carriers of hepatitis B should be closely monitored, including HBV DNA testing. For patients with evidence of prior HBV infection, HBV suppressive therapy with lamivudine, tenofovir, or entecavir is required during treatment and for additional six months after coming off study.

5.4.1.4 Use of Growth Factors and Anti-infection Prophylaxis

The use of colony stimulating factors (CSFs) (e.g., filgrastim, pegfilgrastim, and sargramostim) should be considered for patients who experience febrile neutropenia, prolonged grade 3 neutropenia (>7 days) and grade 4 neutropenia. Other anti-infection prophylaxis (e.g., acyclovir, levofloxacin, and other premedications) will be selected by the Investigator according to local practice and provided by the investigative site.

5.4.1.5 Anti-inflammatory Management

Short courses (≤ 14 days) of corticosteroid treatment for non-lymphoma-related medical reasons (e.g., rash, arthralgia, autoimmune cytopenias and infusion reactions) at doses that do not exceed 100 mg per day of prednisone or equivalent are permitted.

5.4.2 Prohibited Concomitant Medications/Procedures

Any anti-cancer therapy is prohibited 28 days prior to Day 1 dosing and during the entire Treatment Period of the study. Warfarin or equivalent vitamin K antagonists (e.g., phenprocoumon) are prohibited.

5.4.2.1 Acalabrutinib Drug-drug Interactions

Acalabrutinib is not a strong direct inhibitor or inducer or CYP isoforms; thus, acalabrutinib, at the currently used clinical doses, is unlikely to be a perpetrator of a drugdrug interaction at the level of inhibition or induction of CYP isoforms. Acalabrutinib is partially metabolized by CYP3A; its exposure is affected when co-administered with strong CYP3A4 inducers or inhibitors. Consequently, the concomitant use of strong inhibitors/inducers of CYP3A4 (see Appendix D) should be avoided when possible. If medically justified, subjects may be enrolled if such inhibitors or inducers can be discontinued or alternative drugs that do not affect these enzymes can be substituted within 7 days before first dose of study drug. If a subject requires a strong CYP3A4 inhibitor while on study, interrupt acalabrutinib. After discontinuation of strong CYP3A inhibitor for at least 24 hours, resume previous dosage of acalabrutinib. Should a moderate CYP3A inhibitor be required while on study, reduce acalabrutinib dose reduction to 100 mg once daily. If co-

administration of strong CYP3A inducer is unavoidable, increase acalabrutinib dosage to 200 mg every 12 hours.

The effect of agents that reduce gastric acidity (e.g., proton pump inhibitors or antacids) on acalabrutinib capsule absorption was evaluated in a healthy volunteer study. Results from this study indicate that subjects should avoid the use of calcium carbonate-containing drugs or supplements and short-acting H2 receptor antagonists for a period of at least 2 hours when taking acalabrutinib. Specifically, take acalabrutinib 2 hours before taking an H2-receptor antagonist. For antacids, separate dosing by at least 2 hours (before or after taking acalabrutinib). Use of omeprazole, esomeprazole, lansoprazole or any other proton pump inhibitors (e.g., lansoprazole, dexlansoprazole, rabeprazole, or pantoprazole) while taking acalabrutinib is not recommended due to a potential decrease in study drug exposure. Administration of acalabrutinib maleate tablets with acid reducing agents does not impact the absorption; therefore no modification to dosing regimen is necessary.

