3.3 Exclusion Criteria

- Patients with blastoid histology
- Patients with known or suspected CNS involvement
- Viral infection with HIV or hepatitis type B or C. Seropositive HBV patients are eligible if they are negative for HBV DNA by PCR and receive concomitant antiviral therapy during treatment and for additional six months after coming off study.
- Prior history of malignancies other than MCL unless the patient has been disease free for ≥ 5 years from the signing of the ICF. Exceptions include basal cell carcinoma or squamous cell carcinoma of the skin; carcinoma in situ of cervix; carcinoma in situ of breast, or localized prostate cancer
- Active uncontrolled systemic fungal, bacterial or viral infection (defined as ongoing signs/symptoms related to the infection without improvement despite appropriate antibiotics, antiviral therapy and/or other treatment)
- Clinically significant cardiovascular disease such as uncontrolled or symptomatic arrhythmias, congestive heart failure, or myocardial infarction within 6 months of screening, or any Class 3 or 4 cardiac disease as defined by the New York Heart Association Functional Classification.
- Malabsorption syndrome, disease significantly affecting gastrointestinal function, or resection of the stomach or small bowel that is likely to affect absorption, symptomatic inflammatory bowel disease, partial or complete bowel obstruction, or gastric restrictions and bariatric surgery, such as gastric bypass.
- Active bleeding or history of bleeding diathesis (e.g., hemophilia or von Willebrand disease).
- Uncontrolled AIHA (autoimmune hemolytic anemia) or ITP (idiopathic thrombocytopenic purpura).
- Requires treatment with a strong cytochrome P450 3A4 (CYP3A4) inhibitor/inducer. Patients on moderate CYP3A inhibitors can be considered for study after a washout period of at least 7 days.
- Requires or receiving anticoagulation with warfarin or equivalent vitamin K antagonists (e.g., phenprocoumon) within 7 days of first dose of study drug.
- Prothrombin time (PT)/INR or aPTT (in the absence of lupus anticoagulant) $>2x$ ULN.
- Requires treatment with proton pump inhibitors (e.g., omeprazole, esomeprazole, lansoprazole, dexlansoprazole, rabeprazole, or pantoprazole). Subjects receiving proton pump inhibitors who switch to H2-receptor antagonists or antacids are eligible for enrollment to this study.

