5.3 Treatment Administration

5.3.1 Acalabrutinib Administration

Acalabrutinib may be administered in either the tablet or capsule formulation.

Acalabrutinib capsule is administered 100 mg BID and taken orally approximately every 12 hours. The capsules should be swallowed intact with water. Acalabrutinib can be taken with or without food. Subjects should not attempt to open capsules or dissolve them in water. If a dose is missed, it can be taken up to 3 hours after the scheduled time with a return to the normal schedule with the next dose. If it has been > 3 hours, the dose should not be taken and the subject should take the next dose at the scheduled time. The missed dose will not be made up and must be returned to the site at the next scheduled visit.

Patients should avoid the concomitant use of strong inhibitors/inducers of CYP3A4 (see Appendix D) for both capsule and table form of acalabrutinib. Proton pump inhibitors or antacids should be avoided while taking acalabrutinib capsule.

The tablet form of Acalabrutinib is administered at the same dosage and frequency as the capsule. Administration of acalabrutinib maleate tablets with acid reducing agents such as proton

pump inhibitors does not impact the absorption; therefore no modification to dosing regimen is necessary.

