6.2 Acalabrutinib

Dose modifications for the following treatment-emergent toxicities are provided in Table 4:

- Grade 4 neutropenia (< 500/µL) for > 7 days
- Grade 3 thrombocytopenia in presence of significant bleeding
- Grade 4 thrombocytopenia
- Grade 3 or 4 nausea, vomiting, or diarrhea, if persistent despite optimal antiemetic and/or anti-diarrheal therapy

- Any other Grade 4 toxicity or unmanageable Grade 3 toxicity

Table 4. Drug Modification Actions for Acalabrutinib

Occurrence	Action
1 st – 2 nd	Hold acalabrutinib until recovery to Grade \leq 1 or baseline; may restart at original dose level
3 rd	Hold acalabrutinib until recovery to Grade \leq 1 or baseline; restart at one dose level lower (100 mg QD)
4 th	Discontinue acalabrutinib

If acalabrutinib is reduced for apparent treatment-related toxicity, the dose need not be re-escalated, even if there is minimal or no toxicity with the reduced dose. However, if the subject tolerates a reduced dose of acalabrutinib for \geq 4 weeks then the dose may be increased to the next higher dose level, at the discretion of the investigator. Such re-escalation may be particularly warranted if further evaluation reveals that the AE that led to the dose reduction was not treatment-related. The maximum dose of acalabrutinib is 100 mg BID.

Treatment with acalabrutinib should be withheld for any unmanageable, potentially study drug-related toxicity that is Grade \geq 3 in severity. Acalabrutinib should be discontinued in the event of an acalabrutinib toxicity lasting more than 28 day. Any other clinically important events where dose delays may be considered appropriate must be discussed with the Principal Investigator.

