If the outcome of the pregnancy was abnormal (e.g., spontaneous or therapeutic abortion, STILLBIRTH, NEONATAL DEATH, OR CONGENITAL ANOMALY), the Investigator should report the abnormal outcome as an AE. If the abnormal outcome meets any of the serious criteria, it must be reported as an SAE to Acerta Pharma and Celgene Drug Safety immediately by facsimile, or other appropriate method, within 24 hours of the Investigator's knowledge of the event using the SAE Report Form, or approved equivalent form.

All neonatal deaths that occur within 28 days of birth should be reported, without regard to causality, as SAEs. In addition, any infant death after 28 days that the Investigator suspects is

related to the in utero exposure to the IP should also be reported to Acerta Pharma and Celgene Drug Safety immediately by facsimile, or other appropriate method, within 24 hours of the Investigator's knowledge of the event using the SAE Report Form, or approved equivalent form.

Male Subjects

If a female partner of a male subject taking investigational product becomes pregnant while receiving the study drug or within 160 days after the last dose of Rituxan or within 180 days after the last dose of Gazyva, the male subject taking IP should notify the Investigator immediately, and the pregnant female partner should be advised to call their healthcare provider immediately. Male patients treated with IP are advised to continue complete abstinence or condom use during treatment and 28 days after stopping treatment.

Overdose

On a per dose basis, an overdose is defined as the following amount over the protocol-specified dose assigned to a given patient, regardless of any associated adverse events or sequelae.

- PO any amount over the protocol-specified dose
- IV 10% over the protocol-specified dose

On a schedule or frequency basis, an overdose is defined as anything more frequent than the protocol required schedule or frequency.

On an infusion rate basis, an overdose is defined as any rate faster than the protocol-specified rate. Complete data about drug administration, including any overdose, regardless of whether the overdose was accidental or intentional, should be reported in the case report form.

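### Section 5.4.2.1 directs acalabrutinib at 200 mg every 12 hours with an unavoidable strong CYP3A inducer, twice the 100 mg BID maximum stated in section 6.2, and neither section refers to the other

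*Combined protocol and SAP*

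**What the plan says.** **Dose.** Section 5.4.2.1 gives rules for interacting drugs needed during treatment. For a strong inducer that cannot be avoided it reads, in part: "administration of strong CYP3A inducer is unavoidable, increase acalabrutinib dosage to 200 mg every 12 hours". Section 6.2, on acalabrutinib dose modification, ends its paragraph on re-escalation with: "The maximum dose of acalabrutinib is 100 mg BID". The regimens in the Protocol Summary and in sections 5.1.1 and 5.1.2 give acalabrutinib only as 100 mg BID, and Table 7 in section 6.4 has no higher level. Section 5.3.1 mentions no increase; it says: "Patients should avoid the concomitant use of strong inhibitors/inducers of CYP3A4 (see Appendix D) for both capsule and table form of acalabrutinib".

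**Entry.** Section 3.3 (repeated in the Summary) excludes a patient who "Requires treatment with a strong cytochrome P450 3A4 (CYP3A4) inhibitor/inducer". It then adds: "Patients on moderate CYP3A inhibitors can be considered for study after a washout period of at least 7 days". Section 5.4.2.1 allows enrolment of a patient on a strong inhibitor or inducer, when medically justified, if the drug "can be discontinued or alternative drugs that do not affect these enzymes can be substituted within 7 days before first dose of study drug".

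**The concern.** Section 6.2 and section 5.4.2.1 are both places where a site would look up an acalabrutinib dose. A site that checks 6.2 finds a ceiling with no exceptions. A site that checks 5.4.2.1 finds an instruction to go above it. For a patient who comes to need a strong inducer, each site could act differently and each could point to the protocol. The study is multi-center and safety and tolerability of ALR is a secondary objective, so the dose given, and what counts as a deviation, should not depend on which page was read.

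The entry wording matters less. A rule that names a period before the first dose without saying whether it is a minimum leaves the interval for strong interactors to each site, while moderate inhibitors have a clear minimum.

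**Working it through.** No sample-size or error-rate calculation applies. The check is daily-dose arithmetic and a comparison of the texts.

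**1. Daily dose (dose × doses per day).**

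| Source | Wording reduced to figures | Per day |
|---|---|---|
| Section 6.2, stated maximum | 100 mg × 2 | 200 mg |
| Section 5.4.2.1, unavoidable strong inducer | 200 mg × 2 | 400 mg |

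Ratio: 400 / 200 = 2.0 per day, and 200 / 100 = 2.0 per single dose.

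**2. Does either section limit itself or point to the other?** In 6.2, the sentences before the maximum concern raising a dose that had been reduced for toxicity. That suggests a narrower purpose, but the sentence itself has no qualifier and does not mention drug interactions. Section 5.4.2.1 does not mention the maximum or say that it overrides 6.2. The increase appears only in 5.4.2.1. The other dosing text (Summary, 5.1.1, 5.1.2, Table 7) stays at or below 100 mg BID, so nothing elsewhere tells a site that an exception exists.

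**3. Entry timing by drug class.**

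| Class | Where | Minimum interval before first dose, as written |
|---|---|---|
| Moderate CYP3A inhibitor | 3.3 and Summary | at least 7 days |
| Strong CYP3A inhibitor or inducer | 5.4.2.1 | none stated |

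The phrase in 5.4.2.1 can be read in two ways: the change must be complete 7 days ahead, or it must take place at some point in the last 7 days. The literal reading is the second. A stop on the day before the first dose would satisfy it, giving an interval anywhere from about 0 to 7 days. Section 3.3 gives no interval for strong interactors, so it does not settle the question.

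**The case against.** The best defence on the dose is context. The maximum follows directly from text about moving back up a dose level after toxicity, so it can be read as the ceiling for re-escalation, with 5.4.2.1 as the more specific rule for interactions. That reading is reasonable and may be what was intended. It softens the conflict but does not remove it, because the sentence is unqualified and a site would have to infer the hierarchy.

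Three stronger readings are tempting, and the documents do not support them.

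- *That the protocol both excludes and enrols patients on strong interactors.* Section 3.3 excludes those who require such a drug; 5.4.2.1 admits those who can stop or replace it. These rules are complementary. Section 3.3 uses the same pattern for proton pump inhibitors, where a patient who switches becomes eligible. The on-study rules (interruption for a strong inhibitor, a lower dose for a moderate one, a higher dose for a strong inducer) address needs that arise later. They do not conflict with an entry washout.
- *That the 200 mg dose is an overdose by the protocol's own definition.* Section 12.2.2 does say "PO any amount over the protocol-specified dose", but its lead-in ties this to the dose assigned to the individual patient. A dose assigned under 5.4.2.1 is that patient's assigned dose, so calling it an overdose presupposes that 6.2 prevails. The overdose definition needs no change on this ground.
- *That the safety run-in would be distorted.* The documents give no figure for residual inhibition or induction after stopping, nor for how many patients would be affected. No effect on the run-in can be shown from them.

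On entry timing, the two rules cover different drug classes, so they do not collide for any one drug. The documents also do not establish that a strong interactor needs at least the moderate inhibitor's washout. What stands is that the intended interval is unclear.

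**Conclusion.** The dose conflict holds. Sections 5.4.2.1 and 6.2 differ by a factor of 2.0 (400 against 200 mg per day) on what a patient with an unavoidable strong inducer may receive, with no exception or cross-reference. This rests on reading the sentence in 6.2 as worded. If it was meant only for re-escalation, the defect is a missing qualifier, and the amendment is still needed because sites cannot tell.

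The entry-timing point holds as a secondary ambiguity and rests on the literal reading of the phrase in 5.4.2.1. How often either would arise cannot be estimated from the documents, and it may be rare. No view is taken here on which dose or interval is right.

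**What to change.** 1. Reconcile sections 5.4.2.1 and 6.2. Either make the stated maximum and the strong-inducer adjustment agree, or have one section expressly refer to the other and say which governs when a strong inducer is unavoidable.
2. Reword the entry timing in 5.4.2.1 so that the interval intended for strong inhibitors and inducers, counted to the first dose of study drug, has only one reading, and make it consistent with section 3.3 and the Protocol Summary.

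The sponsor and drug supplier decide which values stand. The cost is a wording amendment and a notice to sites, with no added procedures, visits or patients.

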5.5 Duration of Therapy

The study includes an induction phase consisting of 12 cycles of ALR or ALO. Responding subjects will be eligible to enter a maintenance phase. Subjects will continue maintenance ALR or ALO until disease progression, development of unacceptable toxicity, or voluntary withdrawal. Acalabrutinib and lenalidomide can be discontinued after 24 cycles of treatment (12 cycles of induction and 12 cycles of maintenance) for subjects achieving MRD-negative CR during maintenance phase. Subjects have the option to complete study after a total of 3 years of study treatment at the discretion of the treating physician. Subjects can be retreated with acalabrutinib and lenalidomide at time of disease progression.

5.6 Duration of Follow Up

The Follow-up Period for each subject begins upon study treatment discontinuation. A treatment discontinuation safety visit occurs within 28 days of treatment discontinuation. Subjects will be followed for subsequent anti-lymphoma therapies and survival every 6 months according to the schedules described in Tables 1 and 2.

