SCHEMA – ALO FEASIBILITY COHORT

Note

- Treatment includes 12 cycles of induction followed by maintenance. Patients will receive therapy until disease progression, development of unacceptable toxicity, or voluntary withdrawal. Acalabrutinib and lenalidomide can be discontinued after 24 cycles of treatment for subjects achieving MRD-negative CR during maintenance.
- MRD will be measured in peripheral blood at the conclusion of 6 and 12 cycles of induction treatment. Additional MRD measurements in peripheral blood will be collected every 4 cycles during maintenance.
- Imaging studies: PET/CT is required at baseline and time to confirm CR.

STUDY PROCEDURES – ALR

Table 1. Schedule of ALR Study Procedures¹

Procedure	Screening	Treatment Phase							Therapy Discontinuation	Follow-up Phase	
		Cycle 1				Subsequent cycles	Every 3 cycles Year 1	Every 4 cycles Year 2	Every 6 cycles Year 3-5		
		Day 1	Day 8±1	Day 15±1	Day 22±1						
Staging											
Lymph node/tissue biopsy ²	X										
Bone marrow aspirate & biopsy ³	X						Time to confirm CR				
Staging CT scan (or MRI) ⁴	X						X	X	X	X	
PET/CT ⁴	X						Time to confirm CR				
MRD Assay ⁵	X						Cycles 6 & 12	X	Every 6 cycles		
Laboratory Studies											
CBC with differential	X	X	X	X	X	X ¹²				X	
CMP including LFT	X	X	X	X	X	X				X	
LDH, uric acid ¹⁴ , phosphate ¹⁴ , PT/INR ¹⁴ , aPTT ¹⁴	X	X	X	X	X	X				X	
Creatinine clearance ⁶	X										
Thyroid function test TSH, T4, T3 uptake	X						X	X	X	X	
HBsAg, HBsAb, HBcAb, HCV, HIV ⁷	X										
HBV DNA testing ⁷	X						X	X	X	X	
Pregnancy testing ⁸	X	X				X				X	
Buccal Swab / saliva sample ²	X										
Other Evaluations											
Physical examination / vital signs ¹³	X	X	X	X	X	X				X	
Height & weight	X	X				X				X	
ECOG performance status	X	X				X				X	
MIPI score	X										
12-lead ECG ⁹	X										
FACT-Lym QOL questionnaires	X						X	X	X	X	
Concomitant medications	X	X	X	X	X	X				X	
Register Revlimid REMS® program	X										
Prescribe via Revlimid REMS® ¹⁰		X				X					
Adverse events assessment		X	X	X	X	X	X	X	X		
Correlative studies ¹¹		X	X	X	X	X				X	
Obtain Follow-Up treatment										X	

Obtain Follow-Up survival										X
---------------------------	--	--	--	--	--	--	--	--	--	---

¹ Unless otherwise specified, all screening requirements are within 28 days, all other assessments and procedures are +/- 3 days.

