5.2.3 Treatment Discontinuation

At treatment discontinuation, subjects will undergo off study evaluations within 28 days of last dose.

- Physical examination with vital signs and performance status
- AE assessment
- CBC with differential
- Serum chemistries to include TFT, CMP, LDH, phosphate and uric acid
- Concomitant medications
- HBV viral DNA in HBcAb positive, asymptomatic carrier
- Correlative blood samples
- Pregnancy test (for females of childbearing potential)
- CT scan (or MRI) of neck/chest/abdomen/pelvis (and other areas if indicated to evaluate sites of disease involvement); PET scan at discretion of investigator
- FACT-Lym quality-of-life questionnaires
- Telemedicine/virtual visits will be allowed where physical exam and vital signs may not be collected.
- Follow-up contact every 6 months until death

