6.8 Criteria for Removal from Study

Subjects who meet the following criteria should be discontinued from the study:

- Withdraw of consent
- Inability of subject to comply with study requirements
- Determination by the investigator that it is no longer safe for the subject to continue therapy
- Disease progression
- Subject lost to follow-up or death
- Pregnancy or a positive pregnancy test
- Failure to achieve at least PR after 3 cycles (for patients requiring prompt cytoreduction, such as those with bulky or symptomatic disease) or 6 cycles (all others)
- Earlier evidence of nonresponse (including stable disease) that warrants change in therapy in the opinion of the treating physician

Subjects who complete less than 1 cycle of treatment and discontinue treatment for reasons other than toxicity will be replaced.

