9. MEASUREMENT OF EFFECT

9.1 Radiographic Response

Response and progression will be evaluated in this study using the Lugano criteria for lymphoma response.²⁵ The response assessment time points are: every 3 cycles during year 1, every 4 cycles during year 2, and every 6 cycles until disease progression. Subjects should have PET/CT at baseline and at time to confirm CR. If an additional CT scan is performed earlier than the specified time points due to changes in the subject's clinical status, please also perform an additional response assessment at that time. Once a subject has progressed, no further response assessments are required.

PET-CT. PET-CT is the preferred imaging modality for baseline assessment, and for CR confirmation.

Conventional CT and MRI. This guideline has defined measurability of lesions on CT scan based on the assumption that CT thickness is 5mm or less. If CT scans have slice thickness greater than

5 mm, the minimum size of a measurable lesion should be twice the slice thickness. MRI is also acceptable in certain situations.

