11.3.2 Secondary Endpoints

With adequate follow-up time, secondary endpoints of progression-free survival (PFS), overall survival (OS), and time to next treatment will be assessed by Kaplan-Meier survival analysis and 90% confidence intervals will be calculated using Greenwood's formula. PFS will be defined as the time from first treatment day until objective or symptomatic progression or death. OS will be defined as the time from first treatment day until death. TTNT will be defined as time from end of primary treatment to institution of next therapy.

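### After treatment stops, 5.6 and Tables 1 and 2 schedule no progression follow-up while 9.1 runs assessments to progression, and no PFS censoring rule is written; censoring at exit would probably overstate 2-year PFS

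*Combined protocol and SAP*

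**What the plan says.** **After treatment stops.** Section 5.6 starts the follow-up period at treatment discontinuation and lists its content: "Subjects will be followed for subsequent anti-lymphoma therapies and survival every 6 months according to the schedules described in Tables 1 and 2". Section 5.2.3 requires one scan at the discontinuation visit, "CT scan (or MRI) of neck/chest/abdomen/pelvis (and other areas if indicated to evaluate sites of disease involvement); PET scan at discretion of investigator", and then only "Follow-up contact every 6 months until death". The two follow-up rows of Tables 1 and 2 cover later treatment and survival (the latter labelled "Obtain Follow-Up survival").

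**Response assessment.** Section 9.1 sets the schedule as "every 3 cycles during year 1, every 4 cycles during year 2, and every 6 cycles until disease progression" and names progression as the point after which assessments are no longer needed. It does not stop them at the end of treatment.

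**Leaving without progression.** Section 6.8 removes patients for "Failure to achieve at least PR after 3 cycles" (those needing prompt cytoreduction) or after 6 cycles (all others), for earlier non-response including stable disease, and when continuing is judged unsafe. Section 6.3.1 takes a patient off protocol therapy when a new cycle is delayed by more than 4 weeks.

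**Analysis.** Section 11.3.2 states that "secondary endpoints of progression-free survival (PFS), overall survival (OS), and time to next treatment will be assessed by Kaplan-Meier survival analysis", with 90% intervals by Greenwood's formula. Section 1.2 gives PFS a time frame of up to 2 years. Section 9.1.3 counts documented progression or death from any cause; 11.3.2 counts objective or symptomatic progression or death. Neither says what happens at end of treatment, at new therapy or after missed assessments.

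**The concern.** Kaplan-Meier treats a censored patient as having the same later risk as those still under observation. A patient taken off treatment for not reaching a partial response probably has a higher risk of progressing soon afterwards. If progression is not recorded after exit and the patient is censored there, the patients most likely to progress leave the risk set just before their events, and the PFS estimate is too high.

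PFS is a named secondary endpoint, and progression dates not recorded at the time may be hard to recover later. The unwritten rule also leaves a choice to be made after the data are seen, and that choice can move the estimate in either direction.

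**Working it through.** **1. Do the texts conflict?** Column alignment in Tables 1 and 2 is partly lost in the extracted text, but the CT row can still be read. It carries the same four post-screening marks as the HBV DNA row. Footnote 7 decodes those as year 1, year 2, year 3 onward and end of treatment. Footnote 4 gives CT the cycle-based schedule only, and 5.2.3 supplies the discontinuation scan. No scan falls in the follow-up phase. Section 9.1 runs to progression, but in treatment cycles, which a patient off all treatment no longer has. A site could follow either text.

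**2. Is there a plan figure to reproduce?** Not for PFS: the documents give no PFS target, event count or precision. The one design figure, 24 evaluable patients for the primary endpoint, does reproduce. Success at 18 or more of 24 gives exact one-sided alpha 0.096 at 60% and power 0.811 at 80%. This point does not touch it.

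**3. Size of the bias, by exit reason.** All inputs here are assumptions. The doublet's 92% response rate (section 2.2.1) only suggests an upper value of 8% for non-responders.

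- Share *a* = 5-8% leaves for non-response at month *t* = 3 to 5.5, with *h* = 4-10 times the hazard after exit.
- Share *b* = 10-15% leaves for toxicity between months 1 and 18 (midpoint *x* = 9.5), with *g* = 1-2 times the hazard after exit.
- 2-year PFS at the on-treatment hazard is *S* = 0.88-0.90.

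If everyone has the same hazard while on treatment, Kaplan-Meier with censoring at exit estimates *S*. The overstatement is then

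*a*·[*S* − *S*^((*t* + *h*(24 − *t*))/24)] + *b*·[*S* − *S*^((*x* + *g*(24 − *x*))/24)].

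- Low corner (*a* = 0.05, *h* = 4, *t* = 5.5, *S* = 0.90, *g* = 1): exponent 79.5/24 = 3.3125 and 0.90^3.3125 = 0.705, so 0.05 × 0.195 = 0.010. The toxicity term is zero. Total **+1.0 point**.
- High corner (*a* = 0.08, *h* = 10, *t* = 3, *S* = 0.88, *b* = 0.15, *g* = 2): exponent 213/24 = 8.875 and 0.88^8.875 = 0.322, so 0.08 × 0.558 = 0.0447. For toxicity, exponent 38.5/24 = 1.604 and 0.88^1.604 = 0.815, so 0.15 × 0.065 = 0.0098. Total **+5.4 points**.

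Most of the high figure comes from the non-responders. If their higher hazard applies from day 1, the overstatement is somewhat smaller, because some excess events occur before exit and are counted.

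**4. Dependence on the rule.** Take the 28 ALR patients and let *f* = *k*/28 stop without progression at month 6. Assume the others have 2-year PFS of 85% (the doublet's figure in section 2.1, borrowed as a scenario value) and that stoppers have a median PFS *m* of 6 or 24 months from stopping.

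- True value: (1 − *f*)·0.85 + *f*·2^(−18/*m*)
- Censor at stop: [*f* + (1 − *f*)·0.85^(6/24)]·0.85^(18/24)
- New therapy as an event, if all stoppers start it at month 6: (1 − *f*)·0.85

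| *k* | True, *m* = 6 / 24 | Censor at stop (error) | New therapy as event (error) |
|---|---|---|---|
| 1 | 82.4% / 84.1% | 85.1% (+2.7 / +1.0) | 82.0% (−0.4 / −2.1) |
| 2 | 79.8% / 83.2% | 85.3% (+5.4 / +2.1) | 78.9% (−0.9 / −4.2) |
| 4 | 74.6% / 81.4% | 85.5% (+10.9 / +4.2) | 72.9% (−1.8 / −8.5) |

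If the hazard after stopping equals the on-treatment hazard, then for *k* = 4 the true value is 0.7286 + 0.85^0.75/7 = 0.855. Censoring gives the same value, so its error is zero. Counting new therapy as an event then gives −12.6 points.

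**5. Scale.** The 90% half-width at 85% with 28 patients and no censoring is 1.645 × √(0.85 × 0.15/28) = 0.111, about 11 points.

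**The case against.** A reader might infer that the plan collects no information bearing on PFS after exit, and that PFS is therefore definitely biased upward. The documents do not support that.

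- Section 9.1 ends assessments only at progression, so the imaging position is a contradiction, not a settled absence.
- Patients have a scan at discontinuation.
- Deaths after exit count under both definitions, symptomatic progression counts under 11.3.2 if someone records it, and the start of new therapy is collected.
- No text says that patients are censored at exit. The direction depends on that unwritten rule and on the hazard after exit, and for toxicity exits the bias may be nil.
- The hazard multiples and the toxicity exit rate have no source in the documents. Some non-responders will have progressed and are ordinary events.

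A reader might also infer a planned PFS comparison with the doublet's 85%. Section 11 plans none; its historical benchmark is a 60% response rate. Finally, PFS is secondary and untested in an exploratory trial, and an error of 1 to 5 points is smaller than the sampling uncertainty.

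All of this stands and limits the claim. It does not remove the gap. A site that follows 5.6 and the tables has no scheduled progression assessment after exit, and a wide interval does not correct an avoidable bias. Two other groups add nothing to the problem: patients who stop only the oral drugs after cycle 24 stay on antibody and on the scan schedule, and the 3-year completion option falls after the 2-year window.

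**Conclusion.** The point holds in conditional form. Sections 5.6 and 5.2.3 and Tables 1 and 2 schedule no progression assessment after the discontinuation scan, which conflicts with 9.1, and no PFS censoring rule is written. If 5.6 and the tables are followed and patients who leave without progression are censored at exit, 2-year PFS is likely to be overstated, mainly through those removed for non-response.

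The size is about +1 to +5 points under the assumed exit shares and hazards in step 3. It is larger if more patients stop early and do badly, zero if stopping carries no extra hazard, and possibly negative if new therapy is counted as an event. The primary endpoint and its sample size are unaffected. This should be corrected before analysis, but it does not threaten the trial's main conclusion.

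**What to change.** 1. Reconcile 5.6, 5.2.3 and Tables 1 and 2 with 9.1, so that they say the same thing about progression assessment in patients who stop treatment without progression.
2. At the existing 6-monthly contact, record progression status, its date and its basis (routine-care imaging or clinical assessment) for each such patient, and count it in PFS. The same field serves both cohorts.
3. In 11.3.2, state the PFS censoring rule for end of treatment, new anti-lymphoma therapy and missed assessments. Leaving treatment should not by itself be a reason for censoring. Use one definition of progression in 9.1.3 and 11.3.2.
4. Add a sensitivity analysis in which new anti-lymphoma therapy before documented progression counts as a PFS event. The start of new therapy is already needed for time to next treatment.

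The cost is one form field, a few sentences and one analysis, with no added protocol scans or visits. The drawback is that routine-care scans are less regularly timed than those on treatment, so progression dates after exit will be less precise.
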